Visit (V)	V01	PC1	V02	PC2	V03	PC3	V04	V05*	PC4	V06	PC5 6-month safety follow-up
Trial timelines (approximate # of days [D])	D0	D8	D60	D68	D120	D128	D150	D300-390	D308	D330-420	D480-570
Visit / Phone contact intervals		V01 + 8	V01 + 60D	V02 + 8D	V02 + 60D	V03 + 8D	V03 + 30D	V03 + 180D*	V05 + 8D	V05 + 30D	V05 + 180D
Time windows (days)		+2	±14	+2	±14	+2	+14	±14	+2	+14	+14
Approximate age of subjects (months)	2		4		6		7	12-15		13-16	18 - 21
Informed consent	X										
Inclusion/exclusion criteria	X										
Collection of demographic data/body stature	X										
Medical history	X							X			
Vaccination history	X										
Physical examination and temperature†	X		X		X		X	X		X	
IRT contact	X		X		X			X			
Randomization/allocation of subject number	X										
Blood sampling (BL)‡ (approximate volume)								BL0002 (6 mL)	BL0003 (6 mL)		BL0004 (6 mL)
Injection (SP0202 or Prevnar 13)	X		X		X			X			
Routine pediatric vaccines											
Pentacel	X		X		X			-			
RotaTeq	X		X		X			-			
M-M-R _{II} and Varivax	-		-		-			X			

Visit (V)	V01	PC1	V02	PC2	V03	PC3	V04	V05*	PC4	V06	PC5 6-month safety follow-up
Trial timelines (approximate # of days [D])	D0	D8	D60	D68	D120	D128	D150	D300-390	D308	D330-420	D480-570
Visit / Phone contact intervals		V01 + 8	V01 + 60D	V02 + 8D	V02 + 60D	V03 + 8D	V03 + 30D	V03 + 180D*	V05 + 8D	V05 + 30D	V05 + 180D
Time windows (days)		+2	±14	+2	±14	+2	+14	±14	+2	+14	+14
Approximate age of subjects (months)	2		4		6		7	12-15		13-16	18 - 21
Other pediatric vaccine ENGERIX-B§	X		X		X			-			
30-Minute observation period	X		X		X			X			
Telephone contacts		X**		X**		X**			X**		X††
Diary card (DC) provided collected	DC1		DC2 DC1		DC3 DC2		DC4 DC3	DC5 DC4		DC5	
Memory aid (MA) provided checked										X	X
Injection Site Reactions & Systemic Events Assessment	Solicited injection site and systemic reactions: Day 0–7 after each injection Unsolicited adverse events: Day 0–30 after each injection										
Collection of reportable concomitant medications	X		X		X		X	X			
Trial termination record							X			X	
Reporting of SAEs and AESIs	Throughout the trial										

* V05 can take place up until subject reaches 15 months.

† Mandatory at injection Visit (before injection). For other visits: physical examination and temperature measurement will be performed if necessary, based on the health status of the subject.

‡ BL0003 is to be collected prior to injection of study and concomitant vaccines.

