Solicited injection site and systemic reactions will be collected from D0 to D7 following injection. Unsolicited events will be collected from D0 to D30 following injection. SAEs and AESIs will be collected throughout the study (from D0 until the 6-month follow-up safety phone contact).

For both toddlers and infants, anaphylaxis/hypersensitivity, convulsions (including febrile convulsions), hypotonic-hyporesponsive episode, and apnea will be considered as AESIs.

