Note: If D8 falls on a weekend or a holiday, the telephone call may be made on the following business day.

- 1) Record relevant information concerning the subject's health status on the telephone contact form. If an SAE occurred, follow the instructions in [Section 10](#) for reporting it.
- 2) Remind the parent / guardian to do the following:
 - Complete the Day 0–7 pages of the DC5
 - Complete the remaining pages of the DC5, and bring them to V06
 - Notify the site in case of an SAE

Visit 6 (30 [+14] days after Visit 5): Collection of Safety Information and Blood Sample

- 1) If the DC5 information from Day 0–7 has not yet been obtained, obtain it at this time by interviewing the parents. Review the pages of the DC5 with the parent / guardian, including any AEs, medications, or therapy that occurred since vaccination.
- 2) Check medications and record reportable ongoing medications. Review temporary contraindications for blood sampling. Ensure the subject has not had any antibiotics within the previous 72 hours (3 days).
- 3) Conduct a physical examination and take subject's temperature if necessary, based on the health status of the subject.
- 4) Obtain the blood sample (BL0004 – 6 mL) (see [Section 7.1](#) for detailed instructions regarding the handling of blood samples).
- 5) Record the study termination.
- 6) Complete the source document and the relevant CRFs for this visit.
- 7) Complete the end of study CRF of the CRB.
- 8) Provide the memory aid (MA) to the subject's parent / guardian

Safety Follow-up Telephone Call (D 480 - 570 + 14 days)

The investigator or authorized designee will:

- 1) Ask the parent / guardian if the subject has experienced any SAE or AESI in the time since vaccination
- 2) Complete the relevant CRF for this phone contact.

A follow-up visit can be arranged depending on the information recorded during the phone call.

Follow-up of subjects with Related AEs or with AEs That Led to Study/Vaccination Discontinuation:

Unless a subject or subject's parent/guardian refuses further contact, each subject who experiences an AE (whether serious or non-serious) during the study must be followed until the condition resolves, becomes stable, or becomes chronic (even after the end of the subject's participation in the study) if *either* of the following is true:

- The AE is considered by the Investigator to be related to the product administered.

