6.7 Concomitant Medications and Other Therapies

At the time of enrollment, ongoing medications and other therapies (eg, blood products) should be recorded in the source document as well as new medications prescribed for new medical conditions / AEs during study participation.

Documentation in the CRB of ongoing concomitant medication(s) will be limited to specific categories of medication(s) of interest beginning on the day of first vaccination. This may include medications of interest that were started prior to the day of vaccination.

Reportable medications will be collected in the CRB from the day of each vaccination to the end of the solicited and unsolicited follow-up period.

Reportable medications include medications that impact or may impact the consistency of the safety information collected after any vaccination and/or the immune response to vaccination. Three standard categories of reportable medications are defined:

- Category 1: medications impacting or that may have an impact on the evaluation of the safety (eg, antipyretics, analgesics, and non-steroidal anti-inflammatory drugs [NSAIDs], steroids/corticosteroids [therapy duration for less than 2 consecutive weeks])

Note: Topical steroids (Inhaled, otic, ophthalmic, nasal etc.) should not be captured or reported.

- Category 2: medications impacting or that may have an impact on the immune response (eg, other vaccines [including influenza vaccine in the 2 weeks [14 days] preceding or following any study vaccination], blood products, antibiotic classes taken within 3 days [72 hours] prior to blood draw that may interfere with bioassays used by the GCI department, immune-suppressors, immune-modulators with immunosuppressive properties, anti-proliferative drugs such as DNA synthesis inhibitors, immune globulins preceding in the 3 months preceding any vaccination for infants)

Note: Topical antibiotics (Inhaled, otic, ophthalmic, nasal, etc.) should not be captured or reported.

- Category 3: medications impacting or that may have an impact on both the safety and the immune response (eg, long-term systemic corticosteroid therapy [prednisone or equivalent for more than 2 consecutive weeks])

Note: Topical steroids (Inhaled, otic, ophthalmic, nasal etc.) should not be captured or reported.

The information reported in the CRB for each reported medication will be limited to:

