9.1.1.3.3 Unsolicited Adverse Events

In addition to recording solicited reactions, parents / guardians will be instructed to record any other medical events that may occur during the 30-day period after vaccination for toddlers / between the vaccination and the next visit for infants to be taken as per the study design. Space will be provided in the diary card for this purpose.

Information on SAEs will be collected and assessed throughout the study, from inclusion (D0) until 6 months after the last vaccination. Any SAE occurring at any time during the study will be reported by the Investigator in the CRB according to the completion instructions provided by the Sponsor; this includes checking the “Serious” box on the AE CRF and completing the appropriate Safety Complementary Information CRFs. All information concerning the SAE is to be reported either as part of the initial reporting or during follow-up reporting if relevant information became available later (eg, outcome, medical history, results of investigations, copy of hospitalization reports). In case a subject experiences febrile convulsion (neurological event associating fever and seizure), the assessment will be performed according to the “Guideline for definition and collection of cases of febrile convolution”, and this event will be considered an SAE.

See [Section 10](#) for further details on SAE reporting.

For each unsolicited AE (whether serious or non-serious), the following information is to be recorded:

- Start and stop dates^a
- Intensity of the event:

For measurable unsolicited AEs that are part of the list of solicited reactions, the size of the AE as well as the temperature for fever will be collected and analyzed based on the corresponding scale used for solicited reactions (see [Table 9.1](#) and [Table 9.2](#)).

All other unsolicited AEs will be classified according to the following intensity scale:

^a The stop date of all related AEs will be actively solicited. For other events, the investigator will provide the stop date when it becomes available. AEs for which no stop date was obtained during the course of the study will be considered as ongoing at the end of the study.

- Grade 1

CRB: A type of adverse event that is usually transient and may require only minimal treatment or therapeutic intervention. The event does not generally interfere with usual activities of daily living.

DC / eDC: No interference with usual activities.

- Grade 2

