12.2.3 Per-Protocol Analysis Set

The per-protocol analysis set (PPAS) is a subset of the FAS. Three PPAS will be defined: one for Toddlers (PPAS1), one for Infants at Primary series (PPAS2) and one for Infants at Booster (PPAS3).

The subjects presenting with at least one of the following relevant protocol deviations will be excluded from the PPAS1-Toddlers:

- Subject did not meet all protocol-specified inclusion criteria or met at least one of the protocol-specified exclusion criteria
- Subject did not receive vaccine
- Subject received a vaccine other than the one that he / she was randomized to receive
- Preparation and / or administration of vaccine was not done as per-protocol
- Subject did not provide the post-dose serology sample V02 in the proper time window or a post-dose serology sample was not drawn
- Subject received a protocol-prohibited medication or vaccine (identified among category 2 and 3, see [Section 6.7](#))

In addition to the reasons listed above, subjects will also be excluded from the PPAS1 if their V02 serology sample did not produce a valid serotype specific IgG test result (ie, results for all serotypes are missing).

The subjects presenting with at least one of the following relevant protocol deviations will be excluded from the PPAS2 Infants Primary series:

- Subject did not meet all protocol-specified inclusion criteria or met at least one of the protocol-specified exclusion criteria
- Subject did not complete the vaccination schedule
- Subject received a vaccine schedule other than the one that he / she was randomized to receive
- Preparation and / or administration of vaccine was not done as per-protocol
- Subject did not receive vaccine in the proper time window
- Subject did not provide the post-dose serology sample V04 in the proper time window or a post-dose serology sample was not drawn
- Subject received a protocol-prohibited medication or vaccine (identified among category 2 and 3, see [Section 6.7](#))

In addition to the reasons listed above, subjects will also be excluded from the PPAS2 if their V04 serology sample did not produce a valid serotype specific IgG test result (ie, results for all serotypes are missing).

The subjects presenting with at least one of the following relevant protocol deviations will be excluded from the PPAS3-Infants Booster dose:

- Subject did not meet all protocol-specified inclusion criteria or met at least one of the protocol-specified exclusion criteria

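### The medication-collection period in Protocol 6.7 does not match the category 2 look-backs on which the per-protocol exclusions depend

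*Protocol*

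**What the plan says.** Protocol 6.7 sets the recording period: "Reportable medications will be collected in the CRB from the day of each vaccination to the end of the solicited and unsolicited follow-up period". Protocol 5.1.3 gives the end of that follow-up: "Unsolicited events will be collected from D0 to D30 following injection".

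The same section 6.7 lists category 2 products, those that may affect the immune response. Several are defined by looking back from a later event:
- "influenza vaccine in the 2 weeks [14 days] preceding or following any study vaccination";
- antibiotics in the 72 hours before a blood draw;
- for infants, immune globulins in the 3 months before any vaccination.

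Other vaccines and blood products are listed without a window.

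Protocol 12.2.3 removes a subject from PPAS1, PPAS2 or PPAS3 under the rule "Subject received a protocol-prohibited medication or vaccine (identified among category 2 and 3", with a pointer to 6.7 and no time limit. SAP 5.2.1 repeats the rule, running it to V04 for PPAS2 and over the booster phase for PPAS3. SAP 5.2.5 puts the per-protocol analysis first for immunogenicity, followed by the FAS.

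At the visits, Protocol 5.1.4 tells sites: "Check medications and record reportable ongoing medications". The table row "Collection of reportable concomitant medications" is marked at V01 to V05 in both infant tables, and in SAP Tables 3.4 and 3.5, but not at V06.

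**The concern.** An exclusion rule can act only on what has been recorded. If recording stops at Day 30 after each dose, an exposure shortly before the next dose or draw need not be in the CRB, although it is what category 2 describes. A single influenza or other vaccine, or one infusion of immune globulin or a blood product, is also not an ongoing medication, so the visit instruction does not clearly bring it in.

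The per-protocol sets come first in the primary IgG analyses. Their purpose is to show the response free of such exposures. If the entries are absent, subjects whom the rule should remove stay in, and nothing in the data shows it.

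**Working it through.** The plan gives no figure of its own on this point. Its visit days are consistent: 60 + 60 = 120, 120 + 30 = 150, 120 + 180 = 300, 300 + 30 = 330.

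**Inputs**
- End of the recording period: Day 30 after each dose (6.7 with 5.1.3).
- Doses 2 and 3: 60 ± 14 days after the previous dose (5.1.4), so Day 46 to Day 74.
- Dose 4 and BL0003: 180 ± 14 days after Dose 3, and V05 may be later, up to 15 months of age (5.1.4). The earliest day is 180 − 14 = 166.
- Look-backs: influenza vaccine 14 days, antibiotics 3 days, immune globulins 3 months (6.7); other vaccines 4 weeks = 28 days (temporary contraindication, 5.2.7.1).
- Assumption: 3 months is taken as 90 days.

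**Formula.** For an event on day *e* after the previous dose, a look-back of *L* days starts on day *e* − *L*. If *e* − *L* > 30, the whole look-back lies after the recording period.

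| Look-back | Before Dose 2 or 3 | Before Dose 4 or BL0003 |
|---|---|---|
| Influenza vaccine, 14 days | 46 − 14 = 32 to 74 − 14 = 60: wholly outside on all 74 − 46 + 1 = 29 permitted days | 166 − 14 = 152: wholly outside |
| Other vaccines, 28 days | earliest visit: Days 31–45, 15 of 28 days outside; latest visit: starts Day 46, wholly outside | 166 − 28 = 138: wholly outside |
| Immune globulins, 90 days | earliest visit: Days 31–45, 15 of 90 days outside; latest visit: Days 31–73, 43 of 90 outside | 166 − 90 = 76: wholly outside |
| Antibiotics, 3 days | no draw | BL0003: 166 − 3 = 163: wholly outside |

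The 14 days *after* each dose lie inside Day 0–30, so that half of the influenza rule is covered. A V05 later than Day 166 only moves the look-backs further out.

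The toddler V02 and infant V04 and V06 draws are allowed on Day 30 to Day 44. A vaccine or blood product given between Day 31 and such a draw is also outside the period.

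**What each set needs.** PPAS2 under the SAP runs to V04, so it needs the days from Day 31 to Dose 2, to Dose 3 and to the V04 draw. PPAS1 and PPAS3 need the days from Day 31 to the V02 and V06 draws. Whether PPAS3 also uses the stretch before Dose 4 depends on the reading. Protocol 12.2.3 sets no limit, and category 2 counts influenza vaccine before any study dose. SAP 4.3.4.2 and 4.3.4.3, however, compute the booster phase from V05 to V06.

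**Other checks.** Vaccines before a dose are a temporary contraindication for infants (5.2.7.1). Immune globulins and blood products given after enrolment appear in neither 5.2.7.1 nor 5.2.7.2, so no vaccination check calls for them. Section 5.2.8 names the toddler BL0002 and the infant BL0002 and BL0004 draws, not BL0003, although Visit 5 does include the 72-hour antibiotic check.

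**The case against.** The case against is substantial, and much of it stands.

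- **Section 6.7 does not limit recording to this period in so many words.** It lists the look-back products as reportable, lets medications started before vaccination be entered, and sends newly prescribed medications to the source document throughout participation. The CRF completion instructions are not available here and may go further.
- **Diary review is wider than ongoing products.** Step 1 at toddler V02 and infant V02, V03, V04 and V06 covers medications taken since vaccination. This is real mitigation. It does not say that the products then enter the CRB beyond the 6.7 period, and step 1 at V05, after the longest gap, does not mention medications.
- **Infant follow-up could be read as longer.** Section 9.1.1.3.3 has parents record medical events "between the vaccination and the next visit for infants to be taken as per the study design". That concerns events, conflicts with Day 0–30 elsewhere, and does not clearly reach from V04 to V05.
- **Two exposures have their own entry.** Section 5.2.8 requires a CRB note when a toddler V02 or infant V04 or V06 sample is taken less than 3 days after antibiotics. Section 5.2.9 puts COVID-19 vaccines in the concomitant medications CRF. Both should be left out of the gap.
- **Deviations are tracked separately.** A prohibited vaccine before a dose could surface in monitoring. That is possible, but the exclusion rule points to the category 2 and 3 entries.
- **The V06 omission is clerical.** The Visit 6 text requires both review and recording. A reader might infer from the tables that post-Dose 4 medications have nowhere to be recorded; the text does not support that.
- **Impact is limited.** All analyses are descriptive, and the FAS is reported as well.

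**Conclusion.** The inconsistency is real: the period in 6.7 does not fit its own category 2 definitions, the visit procedures or the per-protocol exclusion rules. Read literally, it misses:
- influenza vaccine in the 14 days before Doses 2, 3 and 4, on every permitted visit day;
- other vaccines, blood products and immune globulins given between Day 31 and the next dose or draw;
- antibiotics in the 72 hours before BL0003, which feeds the pre-Dose 4 means and the PD4/pre-Dose 4 ratios.

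None of the other provisions clearly puts a one-off product given after Day 30 into the CRB, so the per-protocol sets *may* keep subjects whom their rule excludes.

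A reader might go further and conclude that nothing after Day 30 is collected and that the exclusions cannot be applied. The documents do not support that, given the diary review, 5.2.8, 5.2.9 and the parts of the look-backs that fall before Day 30. Nor should the share of calendar days after Day 30 be quoted as the size of the problem. Influenza vaccine more than 14 days from a dose is permitted, 5.2.8 handles antibiotics at the other post-dose draws, and the SAP limits may not use the V04–V05 interval at all.

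The documents give no exposure rates, so the number of subjects affected is unknown. The day arithmetic assumes that follow-up ends at Day 30; the 90-day reading of 3 months affects only the immune globulin row. The point is worth correcting because a stated collection rule does not supply the data for a stated primary-analysis exclusion.

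**What to change.** 1. In Protocol 6.7, record category 2 and 3 medications and vaccines, with start and stop dates, from V01 through the last blood draw (V02 for toddlers, V06 for infants). Keep the Day 0–30 limit for category 1 only.
2. In the visit steps of 5.1.4, replace the instruction about ongoing medications with one to record reportable medications taken since the last visit, V05 included.
3. Add the V06 mark to the concomitant-medication row of both infant tables in the protocol and of SAP Tables 3.4 and 3.5.

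The cost is protocol and CRF-instruction wording and a small amount of extra data entry. Parents already record concomitant medications in the diary cards, so no visit, sample or procedure is added.

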7.1 Sample Collection

At Visits that include a blood draw, 6 mL (at V01 and V02 for toddlers and at V04, V05 and V06 for infants) and 3 mL (at V01 for infants^a) of blood will be collected in tubes provided by or recommended by the Sponsor. Immediately prior to the blood draw, the staff member performing the procedure will verify the subject’s identity as well as the assigned subject’s number and sampling stage on the pre-printed label, and will attach the label to the tube. When vaccination and blood sample collection occur at the same visit and vaccine is given only in one of the arms, blood is to be taken from the limb opposite to the one that will be used for vaccination, if possible.

Optional blood collection for routine screening tests (not part of study) for the US sites only

[figure not shown]
The American Academy of Pediatrics (AAP) recommends blood lead screening as part of routine health supervision for children at 9 to 12 MoA and, if possible, again at 24 months of age. Further, the AAP recommends universal screening for anemia at approximately 12 MoA with determination of hemoglobin concentration and an assessment of risk factors associated with iron deficiency and iron deficient anemia ([41](#)). Children enrolled in this study will undergo routine screening outside of the study. Collection of blood for lead and anemia screening could be done at the same time as blood is drawn for the study immunologic assessment via the same venipuncture. This collection should be done in sample tubes which are not part of the study, and as per standard

^a Not applicable from protocol Version 5.0

of care. The results of these tests will not be part of the study report. Blood collection for these screening tests could be done at any visit in the 2nd year of life, once for complete blood count (CBC) (1 mL) and twice for lead blood levels (2 mL for each test).

7.2 Sample Preparation

Detailed instructions on how to prepare blood samples for assessment of immune response are contained in the Operating Guidelines provided to the site. An overview of the procedures is provided here.

7.3 Sample Storage and Shipment

During storage, serum tubes are to be kept in a freezer whose temperature is set and maintained at -20°C or below. The temperature will be monitored and documented on the appropriate form during the entire study. If it rises above -10°C for any period of time, the Clinical Logistics Coordinator must be notified. See the Operating Guidelines for further details.

Shipments to the laboratories will be made only after appropriate monitoring, and following notification of the Clinical Logistics Coordinator. Sera will be shipped frozen, using dry ice to maintain them in a frozen state, in the packaging container provided by the carrier. Again, temperatures will be monitored. Shipments must be compliant with the United Nations (UN) Class 6.2 specifications and the International Air Transport Association (IATA) 602 packaging instructions.

Samples will be shipped to Global Clinical Immunology (GCI) at Sanofi Pasteur. The address is provided in the Operating Guidelines.

Blood samples will be aliquoted at GCI.

